5.1.1.1 Serious infection

In a Phase I multiple dose study of satralizumab in patients with rheumatoid arthritis (SA-105JP), one case of serious infection, bronchopneumonia (1 of 33 patients), was reported. Serious infection is an identified risk of tocilizumab. In the all-exposure population of tocilizumab, the most common serious infections included pneumonia, urinary tract infection, cellulitis, herpes zoster, gastroenteritis, diverticulitis, sepsis and bacterial arthritis.

Treatment with satralizumab suppresses acute phase reactions (fever, increase in CRP, etc.) induced by IL-6 and accordingly suppresses signs and symptoms associated with infection, which may delay the detection of infections. As a result, it may potentially make the infection more serious.

In the completed double-blind periods of the Phase 3 studies (BN40898 and BN40900), the rates of infections and serious infections in the satralizumab group were not higher than in the placebo group.

Patients with an active infection (excluding fungal infections of nail beds or caries dentium) within 4 weeks prior to baseline will be excluded from this study.

Patients with evidence of active TB (excluding patients receiving chemoprophylaxis for latent TB) will be excluded from this study.

Patients with chronic active hepatitis B or C will be excluded from this study.

Patients who received any live or live attenuated vaccine within 6 weeks prior to baseline will be excluded from this study.

- Satralizumab should not be initiated or administered in patients with active infections.
- Patients should be closely monitored for the development of signs and symptoms of infection, as signs and symptoms of acute inflammation may be lessened due to suppression of the acute phase reactants.
- Patients must be instructed to contact their physician immediately when any symptoms suggesting infection appear, in order to *ensure* rapid evaluation and appropriate treatment.
- If a patient develops a serious infection, administration of satralizumab is to be interrupted until the infection is resolved. The *treating physician* should *conduct a benefit-risk assessment* before resuming treatment with satralizumab.
- Live or live attenuated vaccines should not to be given within 6 weeks prior to baseline and during the course of the study as clinical safety has not been established.

5.1.1.2 Neutropenia and Potential Risk of Infection

Reversible neutropenia was reported in 1 of 33 patients with rheumatoid arthritis in the Phase I multiple dose study (SA-105JP).

In the completed double-blind period of the Phase 3 studies, decreases in neutrophil counts have occurred following treatment with satralizumab, which was not associated

with serious infections. The majority of neutrophil decreases were transient or intermittent.

Patients with a low neutrophil count $<2 \times 10^3/\mu\text{L}$ will be excluded from this study.

Caution should be exercised in patients with a low neutrophil count and appropriate measures (such as interruption of satralizumab) should be considered if neutropenia persists.

Recommended dose interruption based on ANC results is shown in [Table 2](#).

Table 2 Neutropenia Risk Mitigation

ANC (/uL)	Action
>1,000	Maintain dose
500 – 1,000	
• If neutropenia persists, satralizumab should be interrupted until ANC is above 1,000/uL.• If ANC is under 1,000/uL at the previous laboratory test, ANC must be checked before treatment with the satralizumab (e.g., ANC test at site).
<500	Satralizumab should be discontinued.

ANC = absolute neutrophil count.

5.1.1.3 Thrombocytopenia and Potential Risk of Bleeding

Treatment-related reduction in platelet count has been observed in the Phase I multiple dose study with rheumatoid arthritis (SA-105JP), although these were within normal range.

In the Phase 3 studies, decreases in platelet counts have been observed following treatment with satralizumab.

Treatment-related reduction in platelets was not associated with bleeding events in clinical trials.

Patients with a platelet count below $10 \times 10^4/\mu\text{L}$ will be excluded from this study.

Caution should be exercised in patients with a low platelet count and appropriate measures (such as interruption of satralizumab) should be considered if thrombocytopenia persists.

Recommended dose interruption based on PLT count is shown in [Table 3](#).

Table 3 Thrombocytopenia Risk Mitigation

Platelet count (/uL)	Action
>75,000	Maintain dose
50,000 – 75,000	If thrombocytopenia persists, satralizumab should be interrupted until platelet count is above 75,000/uL.
<50,000	Satralizumab should be discontinued.

5.1.1.4 Liver Enzyme and Bilirubin Elevations and Potential Risk of Hepatotoxicity

Reversible elevations of AST and total bilirubin were each observed in 2 healthy subjects and reversible elevation of ALT in 1 healthy subject out of 72 healthy subjects in the Phase 1 single ascending dose study (SA-001JP).

In the Phase 3 studies, mild and moderate elevations of liver transaminases have been observed with satralizumab treatment. Most elevations were $< 5 \times \text{ULN}$ and resolved while on treatment with satralizumab. Elevations of ALT or AST $> 3 \times \text{ULN}$ were not associated with increases in total bilirubin.

It has been reported that IL-6 appears to have a hepatoprotective effect on various forms of liver injury and promotes hepatocyte regeneration. Patients with elevated transaminases ALT or AST $> 1.5x \text{ULN}$ will be excluded from this study.

Liver function markers should be closely monitored when satralizumab is administered, especially concomitantly with hepatotoxic drugs or administered in patients with elevated transaminases.

Recommended dose interruption based on transaminases is shown in [Table 4](#).

Table 4 Hepatic Enzyme Risk Mitigation

AST or ALT values	Action
>1 to 3x ULN*	
• Reduction (if necessary, interruption) of hepatotoxic drugs could be considered.• For persistent increases in this range, satralizumab could be interrupted until AST and ALT is below ULN*.
>3 to 5x ULN	
Laboratory tests (ALT, AST, ALP and TBL) should be repeated within 72 hours to confirm value. The presence of clinical symptoms should be queried. Patients who are far away from the trial site may be retested locally if prompt return to the trial site is difficult. If close monitoring is not possible, the drug should be discontinued.
 
Satralizumab should be interrupted until AST and ALT is below 3x ULN. If at least one of following associated, satralizumab should be discontinued.
 
• Total bilirubin >2x ULN and/or• INR >1.5x ULN and/or• Appearance of fatigue, nausea, vomiting, right upper quadrant pain or tenderness, fever, rash, and/or eosinophilia
>5x ULN	
Laboratory tests (ALT, AST, ALP, and TBL) should be repeated within 72 hours as soon as possible to confirm value. If continued, satralizumab should be discontinued immediately and gastroenterology expert should be contacted.
 
The presence of clinical symptoms should be queried. Patients who are far away from the trial site may be retested locally if prompt return to the trial site is difficult.

ALP= alkaline phosphatase; ALT = alanine aminotransferase; AST = aspartate aminotransferase; INR= international normalized ratio; TBL= total bilirubin; ULN= upper limit of normal.

* ULN or patient's baseline whichever is higher.

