4.3.2.2 Satralizumab: Extension period

Patients who complete the double-blind period (see the section “Length of Study” in PROTOCOL SYNOPSIS) or experience a protocol-defined relapse which is adjudicated by the CEC in the double-blind period can enter the open-label extension period. In the open-label extension period, the patient will receive an SC injection of satralizumab at Week 0, 2 and 4, and Q4W thereafter, *with the last study drug administration on or before 31 December 2021.*

For patients who experienced a protocol-defined relapse which is adjudicated by CEC, satralizumab should start in the stable disease condition (Day 31 or later, where Day 1 is defined as the day of onset of a protocol-defined relapse which is adjudicated by CEC). For patients who completed the double-blind period, satralizumab should start after 4 weeks (\pm 7 days) from the last dosing in the double-blind period.

Patients who experience a relapse during the extension period will continue administration of satralizumab at the discretion of the Investigator.

In the OLE period after Week 48, and in accordance with local regulations, administration of satralizumab prefilled syringes outside of the study site (e.g., self-administration or administration by a caregiver after completing training, administration by the patient’s [local] general physician, or home administration by a mobile nurse) will be allowed in emergency situations such as the SARS-CoV-2 (COVID-19) pandemic.

Following the implementation of Protocol Version 10 and in accordance with local regulations, administration of satralizumab prefilled syringes outside of the study site (e.g., self-administration or administration by a caregiver after completing training, or home administration by a mobile nurse) may be allowed on scheduled study drug administration days that do not require additional assessments that must be performed on site ([Appendix 1](#)).

Guidelines for dosage modification and treatment interruption or discontinuation are provided in Section [5.1](#).

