- Relapse assessment will be monitored and recorded throughout the study.
- Perform EDSS/FSS.
- Visual Function Testing (visual function testing includes visual acuity tests of Snellen and Low-contrast Sloan letter chart. Visual acuity test of Snellen chart is not required if it is implemented with FSS assessment), SF-36, VAS for pain, FACIT-fatigue, mRS, EQ-5D and T25W.

- ZBI which is optional and will be performed (window in days is within ± 28 days) for caregiver who signed informed consent to caregiver burden assessment.
- Performing an MRI scan for exploratory evaluation is optional, will be conducted at selected sites, and will require a separate signature on the informed consent (Window in days is within ± 28 days. Week 48 only.). Only for patients who end the double-blind period by Week 48 of the double-blind period.

PK-PD

- Obtain PK sample
- Obtain PD sample includes IL-6, sIL-6R and hsCRP and anti-AQP4 antibody.

Immunogenicity

- Collect sample for anti-drug antibody

After Week 48, the following procedures will be performed in the Extension Period:

Every 4 weeks

- Administer satralizumab injection (SC) after all other study-related procedures have been performed.
- *In accordance with local regulations, patients may have study drug administered outside of the study site for these visits. In such cases, patients should be followed up through phone calls from the study site to monitor treatment compliance and perform safety and efficacy assessments as described below.*

Safety

- AEs and concomitant medications will be monitored and recorded throughout the study.

Efficacy

- Relapse assessment will be monitored and recorded throughout the study.

Every 12 Weeks

- Administer satralizumab injection (SC) after all other study-related procedures have been performed.
- Perform physical exam.
- Record vital signs.
- Perform pregnancy test for females of child-bearing potential. Serum or urine β -hCG [sensitivity of at least 25 mIU/mL] will be performed.
- Laboratory test: RBC, Hb, HCT, WBC, WBC differentiation, PLT, INR, fibrinogen, total protein, albumin, total bilirubin, ALP, AST, ALT, γ -GTP, LDH, total cholesterol, LDL, HDL, triglyceride, ferritin, BUN, creatinine, CK, Na, Cl, K, Ca, P, complement

(CH50, C3, C4), uric acid, urinary glucose, urinary protein, urinary occult blood, urobilinogen.

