4.7.1.1 Discontinuation of Study Treatment

In addition to the criteria listed above, reasons for withdrawal of the study treatment but which do not preclude the patient remaining in the study include, but are not limited to, if the patient:

- Meets the discontinuation criteria in the risk mitigation and dose modification strategy (see Section [5.1](#)).
- Misses three consecutive doses of study drug on scheduled visits in the double-blind period.
- Experiences two relapses in the open-label extension period with a more severe intensity compared with the last relapse prior to baseline.
Investigator should consult with the Medical Monitor if these relapses meet this criterion.
- Experiences malignancy or a severe allergic or anaphylactic reaction to satralizumab.
- Pregnancy.
- Unacceptable toxicity.

If the patient is unwilling to continue in the study, he/she will be asked to return to the clinic for a Withdrawal visit (see Section [4.5.2.3](#)) and may undergo follow-up assessments (see Section [4.5.2.4](#)). The primary reason for premature study treatment

discontinuation should be documented on the appropriate eCRF. Patients who discontinue study treatment prematurely will not be replaced.

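### Table 4 gives no dose hold and no stopping trigger for ALT/AST above 5x ULN until the value is confirmed, although the >3 to 5x ULN row gives both

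*Protocol*

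**What the plan says.** Table 4 in Protocol Section 5.1.1.4 sets dosing actions by ALT or AST level.

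- **>3 to 5x ULN.** Repeat the liver panel within 72 hours and ask about symptoms; local retesting is allowed. The row then adds "If close monitoring is not possible, the drug should be discontinued". It goes on: "Satralizumab should be interrupted until AST and ALT is below 3x ULN. If at least one of following associated, satralizumab should be discontinued". The listed findings are bilirubin >2x ULN, INR >1.5x ULN, and a set of symptoms and signs that includes eosinophilia.
- **>5x ULN.** The 72-hour repeat, the symptom query and the local retest option appear again. The single dosing instruction is "If continued, satralizumab should be discontinued immediately and gastroenterology expert should be contacted".

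Other sections send the reader back to this table. Section 4.3.2.2 says "Guidelines for dosage modification and treatment interruption or discontinuation are provided in Section" 5.1. Section 4.7.1.1 lists, as its first treatment-specific criterion, a patient who "Meets the discontinuation criteria in the risk mitigation and dose modification strategy", again citing Section 5.1.

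The neighbouring tables treat their most severe category differently. Table 3 (platelets <50,000/uL) says "Satralizumab should be discontinued" without a condition, and Table 2 does the same for ANC <500/uL. For a previous ANC under 1,000/uL, Table 2 adds that "ANC must be checked before treatment with the satralizumab".

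**The concern.** Once a value above 5x ULN is confirmed, its row is rightly the strictest: immediate discontinuation and specialist contact. If the repeat falls to >3 to 5x ULN, the milder row applies in full. The weakness is the interval before confirmation, and the case where the repeat is late or not done.

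Section 5.3.5.6 regards ALT/AST >3x ULN together with bilirubin >2x ULN, without another explanation, as a sign of severe liver injury. For that picture Table 4 requires a hold and discontinuation when ALT is 4x ULN. When ALT is 6x ULN it requires a repeat and a symptom query, and no dosing action follows from the bilirubin or from the answer about symptoms.

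A late or missed repeat is plausible in the extension after Week 48. Dosing stays 4-weekly, and under Section 4.5.3.2 "patients may have study drug administered outside of the study site for these visits". Syringes may be taken home (Section 4.3.3). ALT/AST is scheduled only every 12 weeks (Table 8). In emergencies, safety laboratory tests are done locally where that can be arranged (Section 4.5.2.2).

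**Working it through.** The plan states no figure to reproduce. The check is a comparison of the two rows, a search for a rule elsewhere, and a count of doses.

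**Rows side by side (Table 4)**

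| Provision | >3 to 5x ULN | >5x ULN |
|---|---|---|
| Repeat within 72 h | yes | yes |
| Symptom query | yes | yes, with no linked action |
| Hold not dependent on the repeat | yes, until <3x ULN | no |
| Discontinue for bilirubin, INR or symptoms | yes | no |
| Discontinue if close monitoring is impossible | yes | no |
| Discontinue on a confirmed value alone | no | yes |
| Specialist contact | no | yes, if the elevation continues |

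The >5x row restates the clauses the two rows share and omits the other three. It therefore reads as self-contained, not as an addition to the row above.

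**Is there a rule elsewhere?** Sections 4.3.2.2 and 4.7.1.1 point back to Section 5.1. Section 5.3.5.6 requires reporting within 24 hours and gives no dosing action. Section 4.7.1 and the toxicity criterion in Section 4.7.1.1 leave the decision to judgement. The SAP only tabulates AST and ALT.

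**Doses Table 4 does not stop after a first value >5x ULN**

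Inputs: 120 mg per dose every 4 weeks; injection after the other procedures at the visit (Section 4.5.3.2); 14-day minimum interval (Section 4.3.2); repeat within 72 h = 3 days; central laboratory (Section 4.5.1.10); ALT/AST every 4 weeks to extension Week 48 (Table 7) and every 12 weeks afterwards (Table 8). Laboratory turnaround r is not given. T is the dosing visit at which the sample is drawn, so later doses fall at T+28, T+56 and T+84 days.

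1. *Repeat on time.* Margin before the next dose = 28 − 3 − r = 25 − r days. For an assumed r of 1 to 7 days this is 24 to 18 days. At the 14-day minimum it is 14 − 3 − r = 11 − r, or 10 to 4 days. Doses given: 0.
2. *Repeat missed, to extension Week 48.* The next scheduled ALT/AST is at T+28. Assuming no same-day central result, that day's dose is given first: 1 × 120 = 120 mg.
3. *Repeat missed, after Week 48.* The next scheduled ALT/AST is at T+84. The doses at T+28 and T+56 have no scheduled test before them: 2 × 120 = 240 mg. If the T+84 dose also precedes that day's result: 3 × 120 = 360 mg.
4. *Sample from a relapse visit.* The laboratory panel is drawn with no injection (Tables 6 to 8), and treatment may continue after a relapse. If the next dose is d days away, the margin is d − 3 − r. When d is less than 3 + r, a dose can precede the repeat result even if the repeat is on time.
5. *Comparator, >3 to 5x ULN.* The hold applies until ALT/AST is below 3x ULN. Doses given: 0.

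**The case against.** The strongest reply is that other safeguards exist and that the dose counts need a departure from protocol. Section 5.1.1.4 asks for close monitoring of liver markers, especially in patients with raised transaminases. Sections 5.3.5.4 and 5.5.1 make the investigator review every laboratory result and follow each adverse event until it resolves or stabilises. Section 5.1.1.7 allows off-site dosing only if the investigator judges it appropriate, and off-site doses are followed by phone. Reaching 240 to 360 mg requires a missed repeat and none of these safeguards working. Table 4 is also framed as recommended action, and a clinician would naturally read a hold at 4x ULN as implying a hold at 6x ULN.

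Much of this stands as a limit on impact. The counts are worst-case doses under Table 4 as written, not expected exposure. Most Phase 3 elevations were below 5x ULN, and those above 3x ULN were not accompanied by raised bilirubin. The double-blind period is complete, so only extension patients are concerned.

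It does not remove the gap. The safeguards cited are judgement, review, reporting or follow-up, and none is a hold. The milder row is capped at 5x ULN and nothing says its clauses carry upward. At the lower level the sponsor chose explicit rules over discretion. The relapse-visit case needs no missed repeat.

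One practical objection concerns the fix. The 72-hour repeat covers ALT, AST, ALP and bilirubin, so it yields no INR. INR is in the routine haematology panel (Section 4.5.1.10), so a first sample with the full panel supplies that trigger without another draw.

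**Conclusion.** The concern holds. Before confirmation, or if the repeat is late or missed, Table 4 is less protective above 5x ULN than at >3 to 5x ULN, and no other section supplies a dosing rule.

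The effect is 0 doses for a dosing-visit sample repeated on time, 1 dose after a missed repeat up to extension Week 48, and 2 to 3 doses after it. The single dose before Week 48 and the third dose after it rest on the assumption that central results are not available the same day. A relapse-visit sample can also leave a dose uncovered when the next injection is close.

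The documents do not say how many patients had values above 5x ULN or how often repeats are missed, so the number affected cannot be estimated, but it is likely to be small. No efficacy conclusion, error rate or sample-size figure changes. The row should be corrected, but the point does not threaten the trial's validity.

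**What to change.** In the >5x ULN row of Table 4:

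- interrupt satralizumab at once pending the repeat, and do not resume until a repeat result is available;
- carry over the bilirubin, INR and symptom discontinuation triggers from the >3 to 5x row, counting whichever of the first or repeat samples measured them (INR comes from the first sample's routine panel unless it is added to the repeat);
- carry over the clause requiring discontinuation when close monitoring is not possible;
- leave immediate discontinuation and specialist contact on a confirmed value as they are.

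This is a change to one table row, by amendment or site memo, with no added visits or blood draws. The cost is an occasional short dose delay for a value that is not confirmed, which the plan already accepts at 4x ULN. With a dosing-visit sample and an on-time repeat, no dose moves.

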5.1.1.5 Elevated Lipid Levels and Potential Risk of Cardiovascular/Cerebrovascular Events

The slight increases in lipid levels (3 AEs of hyperlipidemia [mild] were observed in 3 out of 33 patients in Phase 1b [SA-105P]) or and no cardiovascular/cerebrovascular events have been observed in Phase 1 trials of satralizumab.

Increases in total cholesterol, LDL cholesterol, HDL cholesterol and triglycerides due to administration of tocilizumab have been observed. However, it is unknown whether these changes were associated with cardiovascular events.

In the Phase 3 studies, elevations in total cholesterol and triglycerides were observed. The elevations in lipid parameters did not require dose interruption.

Patients should be managed according to the guideline such as the National Cholesterol Education Program Adult Treatment Panel III or Japan Atherosclerosis Society guideline.

5.1.1.6 Immunogenicity

In a Phase 1 single-dose study (SA-001JP) of satralizumab in healthy Japanese and Caucasian adult male volunteers, ADA were detected in 39 of the 72 subjects who received satralizumab. Most of ADAs were characterized as neutralizing antibody. In a Phase 1 multiple dose study (SA-105JP) of satralizumab in patients with rheumatoid arthritis, ADA were detected in 2 of the 33 patients who received satralizumab. These ADAs were also characterized as neutralizing antibody, and in these 2 patients, elevation of serum level of satralizumab was not observed.

In the double-blind periods of the Phase 3 studies, ADAs were observed in 41% (Study BN40898) and 71% (Study BN40900) of patients receiving satralizumab. Exposure was lower in ADA positive patients; however, there was no impact of ADAs on safety and no clear impact on efficacy or pharmacodynamic markers indicative of target engagement.

5.1.1.7 Serious Hypersensitivity Reactions

Anaphylaxis and serious hypersensitivity reactions have not been reported in clinical trials with satralizumab treatment; however, anaphylaxis and hypersensitivity reactions are considered a potential risk with all biologic medications, including satralizumab.

Patients with a history of a severe allergic reaction to a biologic agent are excluded from study participation.

The symptoms/signs of hypersensitivity include, but not limited to, blood pressure decrease, dyspnea, loss of consciousness, dizziness, queasiness, vomiting, itchiness, flushing, etc. A decision to continue/discontinue treatment with satralizumab should be made taking into account the risks and benefits if any of these events are observed.

- *Up to Week 48 in the OLE period of the study:*
 - The SC injections should be administered under close supervision in a setting where medications (e.g., corticosteroid, antihistamine and epinephrine) and resuscitation facilities are available
 - Patients should stay in the clinic/hospital at least 1 hour after study treatment administration in order to receive medication immediately if anaphylaxis occurs.

- Patients should be instructed to seek medical attention if they experience symptoms of hypersensitivity reaction outside of the clinic.
- If an anaphylactic reaction or other serious hypersensitivity reaction occurs, satralizumab should be discontinued.
- *Administration of satralizumab prefilled syringes outside of the study site might be allowed (see Section 4.3.2.2) if the investigator determines that it is appropriate. Patients/caregivers should be instructed to recognize the signs and symptoms of hypersensitivity reactions and instructed to seek immediate medical attention if the patient develops symptoms of serious allergic reactions. Patients/caregivers should confirm with the investigator whether treatment with satralizumab may be continued.*

